Patients who interrupted study medication based on the investigator's decision should continue in the study, as per the visits and assessment schedule (see [Section 5.5.5](#)) - interruption of study treatment does not necessarily mandate withdrawal from the study.

Patients who discontinue study medication should NOT be considered withdrawn from the study. The patient should return to the clinic as soon as possible, after discontinuation of study drug, for a study treatment discontinuation visit and then enter the 2-month follow-up epoch. Treatment discontinuation visit assessments detailed in the "treatment discontinuation visit" (TD) in [Table 6-1](#) should be completed and recorded in the CRF. If they fail to return for these assessments for unknown reasons, every effort should be made to contact them as specified in [Section 5.6.4](#). The investigator must determine the primary reason for the patient's premature discontinuation of study treatment and record this information on the Dosage Administration CRF.

After study treatment discontinuation, at a minimum, in abbreviated visits, the following data should to be collected at clinic visits or via telephone visits:

- new / concomitant treatments
- adverse events/Serious Adverse Events

If the patient cannot or is unwilling to attend any visit(s), the site staff should maintain regular telephone contact with the patient, or with a person pre-designated by the patient. This telephone contact should preferably be done according to the study visit schedule.

The investigator must also contact the IRT to register the patient's discontinuation from study treatment.

If study drug discontinuation occurs because treatment code has been broken, please refer to [Section 5.5.9](#).

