2.1 General information

██. Statistical analyses will be performed using SAS® Version 9.3 (or higher).

In general, all data will be reported as observed. No imputation will be performed for the primary efficacy analysis. Supportive and sensitivity analyses are discussed in [Section 2.5.4](#) to evaluate the robustness of primary analysis results.

Descriptive statistics (n, mean, standard deviation [SD], median, minimum, and maximum) will be calculated for continuous data. Minimum and maximum will be presented to the same number of decimal places as reported/collected, 1 additional decimal place for mean and median, and 2 additional decimal places for SD. Derived data will be reported to 1 additional decimal place as the reported data.

Categorical data will be summarized using n and percentages based on the number of non-missing values. Percentages will be presented to 1 decimal place. The number of missing values will be presented as a separate category with no percentage, but only if 1 or more patients are missing data for the summary. Otherwise, all categories will be presented (even if no patients are counted in the category). Counts of zero in any category will be presented without a percentage.

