2.1.1 General definitions

Study drug is defined as any single dose of TIP or placebo administered to the patient as part of the required study procedures.

The date of first dose of study drug is defined as the date of first administration of TIP or placebo; the date of last dose of study drug is defined as the date of the last administration of TIP or placebo.

For dates on or after the date of first dose of study drug, study day is defined as [date of interest – date of first dose of study drug] + 1. For dates before the date of first dose of study drug, study day is defined as [date of first study drug – date of interest].

For each visit, the date recorded by the investigators in the eCRF (variable SVSTDTC in the SDTM SV dataset) will be considered as the visit date in all the algorithms and the listings.

In general, the nominal visits will be used for the by visits summaries. However, for early treatment discontinued patients, data collected at end of treatment (EOT) visit will be mapped to next planned visits after their last scheduled visits before the discontinuation.

Baseline is defined as the last non-missing result prior to the first administration of study drug.

End/last date of study for each patient is defined by the date of last contact as recorded in the database.

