2.5.3 Handling of missing values/censoring/discontinuations

No imputation will be performed for missing data for the primary endpoint.

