The primary efficacy parameter (CFU) will be analyzed using a similar ANCOVA model as used in primary efficacy analysis at Day 85, Day 113 and Day 169. The model will contain treatment, baseline CFU (in log₁₀ unit), and baseline macrolide use (yes/no).

The analysis will not be performed by the subgroup of morphotypes. Six pairwise comparisons will be evaluated as specified in [Section 2.6.3](#). The estimated adjusted treatment difference for each of the 6 comparisons (TIP–placebo) will be displayed along with the associated standard error, 2-sided 95% CI. In addition, CFU data will be summarized by morphotype and sum of all morphotypes at each scheduled visit.

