2.10 Patient reported outcomes

Quality of Life Questionnaire-Bronchiectasis (QoL- B)

QoL-B is assessed at Visit 2 (Baseline), Visit 102 (Day 8), Visit 103 (Day 29), Visit 104 (Day 57), Visit 105 (Day 85), Visit 106 or TD (Day 113), Follow-up Visit 201 (Day 141) and Follow-up Visit 202 or PSD (Day 169).

The QoL-B consists of 37 items across 8 domains: Physical, Role Functioning, Vitality, Emotional Function, Social Functioning, Treatment Burden, Health Perception and Respiratory Symptoms. Each of the 37 items is scored from 1 to 4.

Items in the questionnaire are expressed either 'negatively' or 'positively', therefore a number of items must be recorded before the scores for each of the domains are calculated. The score is calculated by adding the score obtained for each item of a domain (scale), after any necessary recoding. Scoring for each domain can be computed only if at least half the items have been completed. If not, then the domain should not be scored and should be considered missing for that particular person who filled out the questionnaire.

[figure not shown]
[figure not shown]
Descriptive statistics will be provided for each domain score for all applicable visits for the FAS by treatment arm [and](#) pooled arms by continuous and cyclic regimens. Changes from baseline to each post-baseline visit will also be summarized. For the QoL-B Respiratory Symptom Score (RSS), further summaries will be provided for:

- Patients with/without pulmonary exacerbations during the treatment period
- Patients with overall study drug compliance $\geq 80\%$

The change from baseline in QoL-B RSS will be analyzed using a linear repeated measure model. The model will contain treatment, baseline macrolide use, visit (visits 102 to 202), and treatment-by-visit interaction as fixed effects with baseline QoL-B RSS, baseline-by-visit interaction as covariates. The within-patient correlation will be modeled using the unstructured covariance matrix in the mixed model. If the model does not converge, then the compound symmetry covariance structure will be used. The restricted maximum likelihood method will be used.

QoL-B correlation with other patient reported outcome measures will be performed by RTI health solutions; consequently these are not detailed within this SAP.

Details on deriving the domain scores can be found in [Section 5.5](#).

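### Late CFU effects come from separate observed-case ANCOVAs that ignore earlier cultures, so response-related dropout could bias the regimen-versus-placebo contrasts in either direction

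*SAP*

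**What the plan says.** SAP 2.6.3.1 states that CFU "will be analyzed using a similar ANCOVA model as used in primary efficacy analysis at Day 85, Day 113 and Day 169". The terms are given as follows: "The model will contain treatment, baseline CFU" in log10 units, plus baseline macrolide use. There is no visit term and no within-patient correlation, so these read as three separate models. Each gives six contrasts of a TIP arm against pooled placebo.

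On missing data, SAP 2.1 says "In general, all data will be reported as observed", and SAP 2.5.3 says of the model being copied: "No imputation will be performed for missing data for the primary endpoint". SAP 2.6.4 deals only with censoring of time-to-event endpoints. The analyses in SAP 2.5.4 (Wilcoxon and per-protocol) concern the primary endpoint. Protocol 9.4.3 foresees imputation, but within the section on the primary variable, and the SAP carries none of it forward.

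For patients who stop treatment early, SAP 2.1.1 says "data collected at end of treatment (EOT) visit will be mapped to next planned visits after their last scheduled visits before the discontinuation". Protocol 5.6.2 adds: "Patients who discontinue study medication should NOT be considered withdrawn from the study". They return "for a study treatment discontinuation visit and then enter the 2-month follow-up epoch".

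For another longitudinal endpoint the same SAP chooses differently. In SAP 2.10: "The change from baseline in QoL-B RSS will be analyzed using a linear repeated measure model", with treatment-by-visit and baseline-by-visit terms, unstructured covariance, REML and a fallback structure.

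**The concern.** A patient with cultures at Days 8 and 29 but none later contributes nothing to the Day 85 or Day 113 contrast, although those cultures are informative about the missing one. An observed-case ANCOVA is unbiased if, given baseline, macrolide use and arm, having a value is unrelated to the outcome. If patients leave partly because of their CFU response, and do so at different rates in different arms, the contrast shifts.

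The stake is regimen selection. The primary Day 29 analysis pools continuous and cyclical TIP within each cohort, so it cannot separate the regimens. The late models supply the adjusted CFU contrasts that do, and CFU differences by arm go into the forest plots of SAP 2.6.3.

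**Working it through.** **1. The plan's own figures.** None is stated for late CFU. For the primary comparison, SAP section 3 uses difference 2.0, SD 2.0, two-sided alpha 0.05/3, power 90% and about 20% discontinuation.

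- n = 2(z₁₋α/₂ + z₁₋β)²σ²/δ² = 2(2.394 + 1.282)² × 4/4 = 27.0, so 28 per group. The t-test needs 29 (power 0.906), and 29/0.8 = 36.25 against the stated 36.
- Power for 48 against 36, each less 20% (38.4 against 28.8), is 0.942 against the stated 94%.

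Both reproduce, so 2.0 and 2.0 are used below.

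**2. Who has a late value under the mapping rule.**

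| Stops between | TD culture mapped to | Day 85 value | Day 113 value |
|---|---|---|---|
| Day 8 and 29 | Day 29 | no | no |
| Day 29 and 57 | Day 57 | no | no |
| Day 57 and 85 | Day 85 | yes | no |
| Day 85 and 113 | Day 113 | yes | yes |

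Assume a proportion d stops at a constant rate over these four intervals. The share without a value is then 1 − (1 − d)^(2/4) at Day 85 and 1 − (1 − d)^(3/4) at Day 113.

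- d = 20%: 1 − 0.8^0.5 = 0.11 and 1 − 0.8^0.75 = 0.15.
- d = 40%: 1 − 0.6^0.5 = 0.23 and 1 − 0.6^0.75 = 0.32.

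Only the overall 20% is documented, without arm, timing or reason.

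**3. Size of bias.** Large-sample simulation, 200,000 per arm.

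- From the SAP: SD 2.0 and true difference −2.0, held constant over visits.
- Assumed: between-visit correlation 0.3 to 0.7; log-odds of leaving rising 0.5 to 1.0 per SD of the last CFU (zero in the unrelated case); dropout by arm as tabulated. The mapped TD culture is treated as valid for the visit it fills.

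Bias in TIP minus placebo, with mapping (negative favours TIP):

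| Dropout, TIP / placebo | Day 85 | Day 113 |
|---|---|---|
| 20% / 20%, linked to CFU | 0.00 ± 0.01 | 0.00 ± 0.01 |
| 40% / 20%, unrelated to CFU | −0.01 | −0.01 |
| 40% / 20% or 30% / 10%, linked to high CFU | −0.03 to −0.16 | −0.05 to −0.22 |
| 10% / 30%, linked to high CFU | up to +0.14 | +0.05 to +0.20 |
| Same CFU-level rule in both arms (correlation 0.5) | +0.03 to +0.12 | +0.05 to +0.18 |

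In the last row placebo loses more patients because its CFU is higher. An estimate using all earlier visits under missing at random was within about 0.01 throughout.

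These figures read the SD and the correlations as what remains after baseline adjustment. If they are read as values before adjustment, with baseline equally correlated with later visits and fitted as a covariate, the non-zero Day 113 biases shrink to about 0.03 to 0.1 in either direction. The table is therefore the upper range.

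**4. Against the noise.** SE = 2.0 × √(1/n₁ + 1/n₂) for one TIP arm against pooled placebo.

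| n₁ / n₂ | SE | 0.22 / SE |
|---|---|---|
| 24 / 36 (planned) | 0.53 | 0.42 |
| 19.2 / 28.8 (less 20%) | 0.59 | 0.37 |
| 14.3 / 21.4 (107 of 180 randomized) | 0.68 | 0.32 |
| 11.4 / 17.1 (107, less 20%) | 0.76 | 0.29 |

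**5. Day 169.** This was not simulated. Patients who stop drug can still give a Visit 202 culture, but sputum is not in the minimum data set after discontinuation in Protocol 5.6.2, so completeness cannot be inferred.

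**The case against.** The case for leaving the plan alone is substantial.

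- The visit-wise ANCOVA is what Protocol 9.5.1.1 specifies for post-baseline CFU.
- Those who stop drug are not simply lost. They stay in the study, sputum is scheduled at the TD visit and in follow-up, and the TD culture is mapped forward. A reader might infer that everyone who leaves drops out of the late analyses; step 2 shows that only some do.
- Differential dropout is not documented. Protocol 3.2 reports placebo tolerability similar to TIP in earlier cystic fibrosis studies, and within a cohort both regimens use the same number of capsules.
- The agreement of the missing-at-random estimate with the truth is built in, because simulated dropout depended on observed CFU. Such a model also projects leavers from those who stayed. If 30% of a TIP arm stopped and lost the whole effect (an assumption), the effect over all patients would be 0.7 × −2.0 = −1.4, while the model would still return about −2.0.
- With 107 randomized there are about 107 × 24/180 = 14 patients per TIP arm. Seven groups by seven post-baseline visits means 49 means and 7 × 8/2 = 28 covariance parameters. Non-detects set to log10(99) also strain the normality assumption.

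All of this stands, and it limits both the size and the certainty of the point. It does not supply a missing-data analysis for late CFU, and it gives no reason to ignore cultures already collected. It supports adding the model beside the ANCOVA rather than replacing it.

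**Conclusion.** The gap is real and modest. Late CFU is analysed visit by visit on observed data, with no method or sensitivity analysis that uses the earlier cultures of patients without a later one. Bias needs two things together: dropout that differs by arm, and dropout linked to earlier CFU. Under the assumed scenarios it then reaches about 0.2 log10 at Day 113, about a tenth of the planned 2.0 difference and at most 0.3 to 0.4 SE. Otherwise it is about zero.

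A reader might infer that a poorly tolerated regimen will look more effective. The documents do not support that direction. They give no dropout by arm or reason. Tolerability dropout unrelated to CFU produced no bias, and response-driven loss on placebo reversed the sign. Patients who stop producing sputum give only a semi-quantitative swab (Protocol 6.4.1); if they are good responders, their loss would work against TIP.

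The contrasts are secondary and unadjusted for multiplicity, and SAP section 1 regards inference after early closure as exploratory. This is a worthwhile inexpensive improvement and does not touch the primary analysis.

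**What to change.** Add to SAP 2.6.3.1 one mixed model for repeated measures on change in log10 CFU at all post-baseline visits. Include treatment, visit, treatment-by-visit, baseline CFU, baseline-by-visit and macrolide use, with unstructured covariance and REML. Prespecify a fallback structure for non-convergence, as SAP 2.10 does. Its compound symmetry assumes the same correlation between on-drug and off-drug visits, so the choice deserves thought for the cyclical arms.

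Report the Day 85, 113 and 169 contrasts from this model alongside the protocol-specified visit-wise ANCOVA. Say whether mapped TD cultures enter both analyses, and tabulate the number contributing per arm and visit. State that the model assumes missing at random and projects leavers from those who stayed.

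The cost is SAP text, one further model and its output, with no new data. With about 14 patients per TIP arm the unstructured covariance may well need the fallback.

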2.6.3.2 Pulmonary exacerbations

The proportion of patients reporting pulmonary exacerbations during the treatment period, follow up period and across the entire study period will be summarized by cohort and by treatment arm and by pooled arms by regimen for continuous and cyclic regimen

The proportion of patients in each exacerbation category (as defined in [Section 2.6.1.2](#)) will be summarized during the treatment period, follow up period and across the study period by cohort and treatment arm.

Overall and within each pulmonary exacerbation category, the number of events will be summarized during the treatment period and across the study period by cohort and treatment arm.

In addition, summaries of the number and percentage of patients experiencing individual pulmonary exacerbation symptoms will be presented during the treatment period and across the study period by duration of symptoms (> 24 hours and > 48 hours):

- Frequency of each symptom/ finding
- Any two symptoms/ findings that most often occur together and may be combined into one symptom
- Combination of 3 symptoms/findings that occur together in the majority of Pulmonary Exacerbations

Symptoms will be further categorized as follows:

- Sputum/viscosity/purulence > 24h [at least 1 of the 3 symptoms reported as > 24h]
- Malaise/fatigue/lethargy > 24h [at least 1 of the 3 symptoms reported as >24h]
- Shortness of breath at rest/exercise >24 h [at least 1 of the 2 symptoms as >24h]

The number and percentage of pulmonary exacerbations in each category will be presented during the treatment period and across the study period by cohort and treatment arm.

In addition, the number of pulmonary exacerbation signs and symptoms last for more than 48

hours will be summarized separately including below categories.

- Sputum/viscosity/purulence > 48h [at least 1 of the 3 symptoms reported as > 48h]
- Malaise/fatigue/lethargy > 48h [at least 1 of the 3 symptoms reported as >48h]
- Shortness of breath at rest/exercise >48 h [at least 1 of the 2 symptoms as >48h]

Time to first pulmonary exacerbation

The time to first pulmonary exacerbation overall will be analyzed using a Cox regression model stratified by baseline macrolide use. The model will include treatment as a fixed-effect factor, and number of pulmonary exacerbations in the 12 months prior to screening as a covariate. Six pairwise comparisons will be evaluated as specified in [Section 2.6.3](#), in addition two pairwise comparisons will be evaluated between pooled continuous regimens vs pooled placebo and, between pooled cyclic regimens and pooled placebo. The estimated adjusted hazard ratio for TIP over placebo will be displayed along with the associated 2-sided 95% CI. For analyses conducted across the treatment period, patients will be censored at the time of last dose of study drug if they did not have a pulmonary exacerbation during the treatment period. Similarly, for analyses conducted across the study period, patients will be censored at the time of last contact if they did not have a pulmonary exacerbation during the study period.

Kaplan-Meier analysis stratified by cohort and treatment arm and by pooled arms (continuous and alternating regimens) will be also presented and displayed graphically.

The time to first pulmonary exacerbation requiring parenteral antibiotics or hospitalization, and the time to first pulmonary exacerbation requiring hospitalization will also be analyzed using the same approach as described for the time to first pulmonary exacerbation overall.

The exposure adjusted rate of pulmonary exacerbations overall

The exposure adjusted rate of exacerbations will be determined across the treatment period and will be derived as follows:

(Number of pulmonary exacerbations reported during the treatment period / sum of exposure time during the treatment period for all patients during the treatment period) / 365.25

The number of pulmonary exacerbations during the treatment period will be analyzed using a generalized linear model assuming the negative binomial distribution including treatment and baseline macrolide use as fixed-effect factors, and number of pulmonary exacerbations in the 12 months prior to screening as a covariate. The log exposure to treatment in years will be included as an offset variable in the model.

Six pairwise comparisons will be evaluated as specified in [Section 2.6.3](#), in addition two pairwise comparisons will be evaluated between pooled continuous regimens vs pooled placebo and, between pooled cyclic regimens and pooled placebo. The estimated rate ratio along with 2-sided 95% interval will be provided.

The exposure adjusted rate of exacerbations across the entire study period will be derived as follows:

(Number of patients with a pulmonary exacerbation during the study period / sum of study period duration for all patients during the study period) / 365.25.

The number of pulmonary exacerbations during the entire study period will be analyzed in a similar manner as the pulmonary exacerbations during the treatment period; the log time in study in years will be included as an offset variable in the model.

Duration of pulmonary exacerbations overall

The duration of pulmonary exacerbations is defined as the sum of the duration of days recorded as an exacerbation for all exacerbations recorded per patient. This will be derived across the treatment period and across the study period. The duration of pulmonary exacerbations will be analyzed using an ANCOVA model. The model will include treatment as a fixed-effect factor, and number of pulmonary exacerbations in the 12 months prior to screening as a covariate.

Six pairwise comparisons will be evaluated as specified in [Section 2.6.3](#), in addition two pairwise comparisons will be evaluated between pooled continuous regimens vs pooled placebo and, between pooled cyclic regimens and pooled placebo. The estimated adjusted treatment difference for each of the comparisons (TIP–placebo) will be displayed along with the associated standard error, 2-sided 95% CI.

Time to permanent study drug discontinuation due to pulmonary exacerbation

The proportion of subjects who permanently discontinue study drug to pulmonary exacerbation will be summarized by cohort and treatment arm.

The time to permanent study drug discontinuation due to pulmonary exacerbation will be analyzed using a Cox regression model stratified by baseline macrolide use. The model will include treatment as a fixed-effect factor, and number of pulmonary exacerbations in the 12 months prior to screening as covariate. Six pairwise comparisons will be evaluated as specified in [Section 2.6.3](#). in addition two pairwise comparisons will be evaluated between pooled continuous regimens vs pooled placebo and, between pooled cyclic regimens and pooled placebo. The estimated adjusted hazard ratio for TIP over placebo will be displayed along with the associated 2-sided 95% CI.

Patients will be censored at the time of last dose of study drug if they did not discontinue study drug due to a pulmonary exacerbation.

Kaplan-Meier analysis stratified by treatment arm will be also presented and displayed graphically.

